11.3 Safety Reporting Requirements for IND Holders

In accordance with 21 CFR 212.32, sponsor-investigators of studies conducted under an IND must comply with following safety reporting requirements:

1. Expedited IND Safety Reports:

- Seven Calendar-Day Telephone or Fax Report

The Sponsor-Investigator is required to notify the FDA of any fatal or life-threatening adverse event that is unexpected and assessed by the investigator to be possibly related to the use of LEAG. An unexpected adverse event is one that is not already described in the Investigator Brochure. Such reports are to be telephoned or faxed to the FDA within seven calendar days of first learning of the event. Each telephone call or fax transmission (see fax number below) should be directed to the FDA new drug review division in the Center for Drug Evaluation and Research or in the product review division for the Center for Biologics Evaluation and Research, whichever is responsible for the review of the IND.

- 15 Calendar-Day Written Report

The Sponsor-Investigator is also required to notify the FDA and all participating investigators, in a written IND Safety Report, of any serious, unexpected AE that is considered possibly related to the use of LEAG. An unexpected adverse event is one that is not already described in the Investigator Brochure.

Written IND Safety Reports should include an Analysis of Similar Events in accordance with regulation 21 CFR § 312.32. All safety reports previously filed with the IND concerning similar events should be analyzed. The new report should contain comments on the significance of the new event in light of the previous, similar reports.

Written IND safety reports with Analysis of Similar Events are to be submitted to the FDA and all participating investigators within 15 calendar days of first learning of the event. The FDA prefers these reports on a MedWatch 3500A Form but alternative formats are acceptable (e.g. summary letter).

FDA fax number for IND Safety Reports:

[name] ([name])

MedWatch 3500A Reporting Guidelines

In addition to completing appropriate patient demographic and suspect medication information, the report should include the following information within the Event Description (Section 5) of the MedWatch 3500A form:

- Treatment regimen (dosing frequency, combination therapy, administration dates);
- Protocol description (and number, if assigned);
- Description of event, severity, treatment, and outcome, if known;
- Supportive laboratory results and diagnostics; and
- Investigator's assessment of the relationship of the adverse event to each investigational product and suspect medication.

11.4 IND Annual Reports

In accordance with the regulation 21 CFR § 312.32, the Sponsor-Investigator shall within 60 days of the anniversary date that the IND went into effect, submit a brief report of the progress of the investigation. Please refer to the Code of Federal Regulations, 21 CFR § 312.32 for a list of the elements required for the annual report.

12.0 STUDY CALANDER

	Screening	Study Visit One	Follow-up Phone Call	Study Visit Two	Study Visit Three
Informed Consent	X				
LEAG ^A		X-----X			
Surgery				X	
Demographics	X				
Medical History and Physical	X				X
Vital Signs	X	X		X	X
Concurrent Medications	X	X-----X			
Height	X				
Weight	X				
Body mass Index		X			
Performance Status	X	X		X	X
Waist Hip Ratio		X			
Body Composition		X			
Gail Model Risk Assessment		X			
NCI Dietary Questionnaire		X			
Tecumseh Questionnaire		X			
Minnesota Questionnaire		X			
Fasting Blood Draw for Laboratory Studies ^B		X		X	
Platelet Function Assay-100 ^G		X		X	
Adverse Event Evaluation		X-----X			
Radiologic Evaluation ^C	X				
Tissue Collection	X			X	
Pregnancy test ^D	X				
HbA1c/ Blood glucose ^E	X				
Diary ^F					
Capsule Count ^H				X	

A: LEAG must be taken for a minimum of 5 days and no more than 14 days. Final dose to be taken day prior to surgery. Patients are required to keep a Ginseng medication diary.

B: Patients must be NPO after midnight. Draw 40 cc of blood from a vein into vacutainer tubes: 6mL in EDTA, 6mL in Na Heparin, 5mL in clot activator tube, and 24mL in serum tubes. Refrigerate serum tubes at 4°C until centrifugation for serum collection and storage.

C: All radiologic evaluations must be completed within 6 weeks of treatment. (mammogram, ultrasound, and MRI are acceptable)

D: Urine pregnancy test for patients of child bearing potential.

E: Only required in diabetic patients. If an HbA1c has not been conducted within 60 days, a fasting blood glucose finger stick of < 140 mg/dl for 3 consecutive days will be allowed as a substitute for verification of control.

F: Patient must be given a diary for blood pressures and/ or blood glucose by finger stick if they are being treated for hypertension or have been diagnosed with diabetes, respectively. Diaries need only be kept while patient is actively on LEAG (5-14 days). Diaries to be returned to research nurse on day of surgery.

G: The Platelet Function Assay-100 test is only conducted on the first 5 patients enrolled. Draw 2 – 2.7mL citrate tubes.

H: Patients are required to keep a Ginseng medication diary. The diary and pill bottle should be returned the day of surgery.

13.0 DEFINITIONS OF MEASUREMENT

13.1 Diagnostic Disease Parameters for Inclusion in Study

- Measurable disease

Measurable lesions are defined as those that can be accurately measured in at least one dimension (longest diameter to be recorded) as ≥ 0.5 cm with conventional techniques (mammography, MRI, ultrasound). All tumor measurements must be recorded decimal fractions of centimeters.

- Non-measurable disease

All lesions < 0.5 cm using mammography, MRI or ultrasound, are considered non-measurable disease.

All measurements should be taken and recorded in metric notation using a ruler or calipers. All baseline evaluations should be performed as closely as possible to the beginning of treatment and never more than 6 weeks before the day of surgery.

- Mammogram

Lesions on mammogram films are acceptable as measurable lesions when they are clearly defined and surrounded by fatty breast tissue.

- Ultrasound (US)

Ultrasound measurement of tumor is an adjunct to the clinical measurement of palpable breast tumors and lymph nodes and to the mammographic measurement of tumor. When the clinically palpable lesion is larger than the US image, the clinical measurement is primary.

- Magnetic Resonance Imaging (MRI)

14.0 DATA REPORTING / REGULATORY CONSIDERATIONS

14.1 Adverse Events

Adverse event lists, guidelines, and instructions for AE reporting can be found in Section 11.0 (Adverse Events: List and Reporting Requirements).

14.2 Institutional Review Board Approval

This protocol, the informed consent document, and relevant supporting information must be submitted to the IRB for review and must be approved before the study is initiated. In addition, any advertising materials must be approved by the IRB. The study will be conducted in accordance with U.S. FDA, applicable national and local health authority, and IRB requirements.

The Principal Investigator is responsible for keeping the IRB apprised of the progress of the study and of any changes made to the protocol as deemed appropriate, but in any case, the IRB approval must be updated at least once a year. The Principal Investigator must also keep the IRB informed of any significant adverse events.

Investigators are required to promptly notify their respective IRB of all adverse drug reactions that are both serious and unexpected. This generally refers to serious adverse events that are not already identified in the Investigator Brochure and that are considered possibly or probably related to the study drug by the investigator. Some IRBs may have other specific adverse event requirements to which investigators are expected to adhere. Submit IRB information to:

[name]
Southern Illinois University School of Medicine
[name]
[name]
[contact]
E-mail: [contact]

14.3 Sponsor and Investigator Requirements

Sponsors are responsible for selecting qualified investigators, providing them with the information they need to conduct an investigation properly, ensuring proper monitoring of the investigation(s), ensuring that the investigation(s) is conducted in accordance with the general investigational plan and protocols contained in the IND, maintaining an effective IND with respect to the investigations, and ensuring that the FDA and all participating investigators are promptly informed of significant new adverse effects or risks with respect to the drug. Please refer to the Code of Federal Regulations, Title 21, Subpart D, 312.50 through 312.69 at:

<http://www.accessdata.fda.gov/scripts/cdrh/cfdocs/cfcfr/CFRSearch.cfm>.

14.4 Study Initiation

Before the start of this study the following documents must be on file at the Clinical Research Office:

- U.S. Food and Drug Administration (FDA) Form 1572, signed by the Principal Investigator.
 - The names of any sub-investigators must appear on this form. Investigators must also complete all regulatory documentation as required by local regulations.
- Current curricula vitae and license of the Principal Investigator.
- Final Protocol and ICF
- Written documentation of IRB approval of protocol and ICF (identified by title and date of approval) for each site.
- Written documentation from the FDA assigning an IND number to the trial and the approval to begin the study.

14.5 Study Completion

The following data and materials are required to be on file at the Clinical Research Office before a study can be considered complete or terminated:

- Copies of protocol amendments and IRB approval/notification, if appropriate.
- Copies of the IRB final report/termination document, documentation of submission to the IRB and to the FDA.
- A summary of the study prepared by the Principal Investigator (study report, manuscript and/or abstract).
- All regulatory documents (e.g., updated curriculum vitae for each Principal Investigator, updated U.S. FDA Form 1572 for each site).

14.6 Informed Consent

The informed consent documents must be signed by the patient, or the patient's legally authorized representative, before his or her participation in the study. The case history for each patient shall document that informed consent was obtained prior to participation in the study. A copy of the informed consent documents must be provided to the patient or the patient's legally authorized representative. If applicable, they will be provided in a certified translation of the local language.

Original signed consent forms must be filed in the site study binder or in each patient's study file.

14.7 Data Collection

Patient medical information obtained by this study is confidential, and disclosure to third parties other than those noted below is prohibited. Upon the patient's permission, medical information may be given to his or her personal physician or other appropriate medical personnel responsible

for his or her welfare.

Data generated by this study must be available for inspection upon request by representatives of the U.S. FDA, local health authorities, and their authorized representative(s), collaborators and licensees, and the site, if IRB.

All study related data will be kept and locked in the Clinical Research Office at Southern Illinois University School of Medicine. Submission of all study assessments, mammography, blood tests, and body composition results along with all case report forms should be submitted to the Clinical Research Office (CRO) to be placed in the patients study chart in a timely manner. The case report form completion guidelines are as follows:

Retention of Records

U.S. FDA regulations (21 CFR §312.62[c]) require that records and documents pertaining to the conduct of this study and the distribution of investigational drug, including CRFs, consent forms, laboratory test results, and medication inventory records, must be retained by the Principal Investigator for two years after marketing application approval. If no application is filed, these records must be kept two years after the study is discontinued and the U.S. FDA and the applicable national and local health authorities are notified.

Confidentiality/ Data Collection

Patients will be assigned a unique patient identification number upon enrollment. Study data and results will be kept confidential. No personal identification will be used in any publications resulting from this study. Results of the baseline and follow-up assessments will be shared with the subjects and they can request any data to be sent to their primary care physician. All of the data will be collated into a database that will be coded so that individual subjects identities will be known only to the investigators.

Analysis of Safety

With respect to the safety goals of this study, toxicities specific to this therapy are not known at this time. Therefore, patients will be monitored for unexpected toxicities and if any serious side effects are observed, an independent monitoring committee will examine the data and evaluate the appropriate course of the study. At the conclusion of the study, all unexpected toxicities will be summarized and reported.

To evaluate a potential effect of LEAG on platelet function, a Platelet Function Assay-100 test will be conducted on the first five patients enrolled. Platelet function will be assessed prior to LEAG administration and prior to surgery on the day of surgery. All adverse events will be

monitored for 30 days beyond the last dose of LEAG, including bleeding complications. Following completion of the study protocol by 5 patients the Data Safety Monitoring Committee will review the adverse events associated with LEAG administration paying particular attention to platelet function. The committee will make a recommendation on continued monitoring of platelet function or its removal from required study procedures for the remainder of patients enrolled. – See section 5.7.4

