5.7 Study Role-Out: Additional Procedures for the First 5 Patients

Additional procedures will be conducted to evaluate the effects of LEAG on platelet function. The first 5 patients enrolled will have platelet function assessed prior to surgery with an interim analysis of platelet function and bleeding complications prior to additional patient enrollment to determine if platelet function should be evaluated in all study patients. After 5 patients have completed the study protocol a safety meeting will convene to determine if pre-operative assessment of platelet function is needed in all study patients. The following procedures have been added for the first five patients.

- 5.7.1 Added Exclusion Criteria
 - Role-out patients taking aspirin, other anti-coagulants, or anti-platelet aggregate are excluded at this time. Platelet Function Assay -100 may be affected by anti-coagulant use.

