5.7.3 Added post-LEAG but pre-surgical laboratory test

- Repeat Platelet Function Assay-100 test prior to surgery (2 citrate tubes of blood drawn day of surgery)

5.7.4 Interim Analysis of Platelet Function Assay completed following completion of 5 subjects. All PFA-100 results were within normal limits. Recommendations from Data Review Team state that further Platelet Function Assay testing is not necessary.

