7.3.2 Coumadin

- Due to a report concerning the possible interaction between coumadin and ginseng, patients currently being treated with coumadin are ineligible for the study.

All other medications, prescription, and over the counter, that affect platelets and/or clotting functions should be used with caution.

7.3.3 Herbal Supplements and Alternative Medications not approved by the FDA.

- All Herbal Supplements and Alternative Medications not approved by the FDA including oral and external application products are prohibited from use during this study and for six weeks prior to initial biopsy.

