7.3.4 Aspirin, other anti-coagulants, and anti-platelet aggregates

- Aspirin and other anti-coagulants are only prohibited in the first 5 role-out patients until the effects of LEAG on platelet function can be assessed.

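### Minor, cheap improvement: the final safety summary covers only unexpected toxicities, so known ginseng effects and perioperative bleeding can be left out of it

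*Combined protocol and SAP*

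**What the plan says.** Section 14.7, under Analysis of Safety, says that toxicities specific to this therapy are not yet known and that patients will therefore be watched for unexpected ones. It then gives the committee trigger, "if any serious side effects are observed, an independent monitoring committee will examine the data and evaluate the appropriate course of the study", and the reporting commitment, "At the conclusion of the study, all unexpected toxicities will be summarized and reported". The same section has all adverse events, bleeding complications included, monitored for 30 days after the last dose.

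It schedules one review: "Following completion of the study protocol by 5 patients the Data Safety Monitoring Committee will review the adverse events associated with LEAG administration". Item 5.7.4 records the outcome: "All PFA-100 results were within normal limits" and "Recommendations from Data Review Team state that further Platelet Function Assay testing is not necessary". It states no bleeding result.

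Aspirin rules differ before and after that review. Item 5.7.1: "Role-out patients taking aspirin, other anti-coagulants, or anti-platelet aggregate are excluded at this time". Section 7.3.4: "Aspirin and other anti-coagulants are only prohibited in the first 5 role-out patients". After the review, section 7.3.2 says only that other drugs "that affect platelets and/or clotting functions should be used with caution"; coumadin remains barred.

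Four other sections bear on the word *unexpected*:
- 11.1 makes every adverse event either expected or unexpected.
- 7.1 lists reported ginseng effects, among them headache, anxiety, sleep and gastrointestinal disturbance, and changes in blood pressure and blood sugar.
- 11.2 leaves unreported the expected events that were covered in the pre-operative discussion or the surgical consent.
- 11.3 defines unexpected, for FDA reports, as not described in the Investigator Brochure.

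**The concern.** The plan collects more safety data than it commits to summarize. Adverse events are logged on the day of surgery and followed afterwards (5.5, 5.6), and all other drugs are recorded, including over-the-counter ones (7.2). The final summary is then restricted by a label. A headache or sleep disturbance is a listed effect, so it can be classed as expected and left out. A perioperative bleed can be treated as an expected surgical event and left out as well.

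Bleeding matters because the protocol itself raised the question. It paused enrollment for a platelet and bleeding review, and LEAG is taken until the day before surgery. The patients reviewed could not take aspirin, so that review cannot speak to LEAG taken with aspirin. Section 2.6 makes positive results the basis for later LEAG studies, whose designers would want the full adverse event record.

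**Working it through.** **1. What the final summary must contain if the text is followed exactly.**

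| Event | Where it is addressed | Required in the final summary? |
|---|---|---|
| Effect listed in 7.1 | Can be classed as expected under 11.1 | No |
| Surgical or anesthesia event listed in the surgical consent | Not reported under 11.2 | No |
| Perioperative bleed | Monitored under 14.7; class not stated | Depends on the label |
| Event classed as unexpected | 14.7 | Yes |

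No other section widens this. Section 14.5 requires a study summary but sets no adverse event content. Section 16 has no safety analysis. Section 11.4 requires annual IND reports and refers to the regulations for their elements. The surgical consent and the Investigator Brochure are not in the documents, so how a bleed would be classed cannot be settled.

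**2. Patients enrolled after the only scheduled review.** Planned accrual is 25 to 50 (16.1), and five were reviewed (5.7).
- 25 − 5 = 20, and 20/25 = 80%.
- 50 − 5 = 45, and 45/50 = 90%.

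**3. What five normal platelet tests show.** With 0 abnormal of 5, the exact one-sided 95% upper limit is 1 − 0.05^(1/5) = 0.451, or 45%. The chance of 0 of 5 is (1 − p)^5: 77% at p = 5%, 59% at 10% and 33% at 20%. This concerns abnormal tests in patients not taking aspirin. It is silent on LEAG with aspirin.

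**4. Where bleeds would be seen.** The documents give no bleeding rate. The chance of at least one bleed is 1 − (1 − p)^n:

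| Assumed rate p | n = 5 | n = 20 | n = 45 |
|---|---|---|---|
| 5% | 22.6% | 64.2% | 90.1% |
| 10% | 41.0% | 87.8% | 99.1% |

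The useful bleeding information lies in the later patients.

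**5. How much the aspirin split can show.** Aspirin use is not given. At an assumed 10% to 30%, users number 2 to 6 of 20, or 4.5 to 13.5 of 45. With zero bleeds in users, the upper limit 1 − 0.05^(1/m) runs from 77.6% (m = 2) to 19.3% (m = 14, rounded up from 13.5). The split can only be descriptive.

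**6. Collection window.** The last dose is the day before surgery, so 30 days after it is day 29 after surgery. The post-surgery visit is generally on days 10 to 20 (5.6.4). That leaves 29 − 20 = 9 to 29 − 10 = 19 days in which 5.6.1 collects only related or possibly related events, while 14.7 says all events are monitored.

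**The case against.** The strongest reply is that 14.7 calls LEAG-specific toxicities unknown, so any toxicity would count as unexpected and nothing would be lost. That reading does not fit 7.1, which lists reported effects, or 11.1, which requires each event to be classed one way or the other. It is fair to add that 14.7 does not forbid reporting more, and that the Brochure definition in 11.3 was written for FDA reports. The point therefore concerns what the plan commits to. It does not show that events will be suppressed.

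The 11.2 exemption can also be read as limited to reports to the IRB, since it sits among those instructions. That is plausible, and one sentence would make it certain.

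It is also true that the aspirin table will be small, has no control arm, and will contain ordinary surgical bleeding. Some regular aspirin users may be kept out by the exclusion of chronic anti-inflammatory drugs (3.2). All of this stands, and it limits the table to description.

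A reader might infer that the committee trigger is also too narrow. The documents do not support that. Any one serious side effect brings the data to the committee, grade 3 or higher toxicity is a reason to stop treatment (6.6), and IRB and FDA reporting continue (11.2, 11.3). Forwarding every bleed without a threshold would mostly add load.

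**Conclusion.** The point holds as a minor improvement. The end-of-study commitment is narrower than the data collected, and whether known effects or perioperative bleeding appear in it depends on a classification. The 80% to 90% of patients enrolled after the review have no other stated end-of-study safety summary.

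The textual conclusion needs no assumed rate. The bleeding rates and aspirin shares in the working are assumptions, used only to show that the later patients carry the information and that a split by aspirin use cannot support a test.

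A reader might also infer that LEAG with aspirin is unsafe, or that stopping the platelet test was wrong. Neither is shown. The antiplatelet statement in 6.4 follows small animal tests, and of the three ginsenosides it names (Ro, Rg1, Rg2) only Rg1 is in the product table. Coumadin, active bleeding and high bleeding risk stay excluded (3.2), and caution applies to other clotting drugs.

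**What to change.** In section 14.7, replace the end-of-study sentence with a commitment to:
- summarize all recorded adverse events by grade, expectedness and attribution;
- list all recorded bleeding complications by aspirin or anti-platelet use, taken from the concomitant medication log (7.2), descriptively and without a test.

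Add that the 11.2 exemption governs reports to the IRB and does not limit this summary. Reconcile 5.6.1 with 14.7 on collection between the post-surgery visit and day 30. If follow-up is already finished, state in the summary that unrelated events in that interval may be incomplete.

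The cost is a few sentences and one more table. No visit, test or patient is added, and no sample size or error rate changes. The change works even if accrual has ended, because it uses records already held. Accrual may well have ended: version 1.8 (June 2018) revised the objectives for data availability about 103 months after version 1.6 (October 2009), against 72 months planned in the Synopsis. That is inference, since no accrual dates are given.
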